	
For confidence interval involving binary outcomes, the Cochran-Mantel-Haenszel weights will be used to combine the stratum-specific differences where the strata will be based upon the factors used to assign subjects to treatment for involving continuous outcomes, the stratum-specific differences will be combined using an analysis of variance approach with weights proportionate to the stratum sizes.
 
Other secondary continuous variables will be summarized using descriptive statistics (N, mean, standard deviation, 95% confidence interval, median, range, minimum, and maximum, where appropriate). Discrete variables will be summarized using frequency counts and percentages.
 
Starting with Treatment Period 2, data summaries for efficacy will be presented by the particular treatment sequence received in Treatment Periods 1 and 2: CHS-1420/CHS-1420, Humira/Humira and Humira/CHS-1420. Safety data for Treatment Period 1 will be presented by the treatment received. Safety data for the study period as a whole (ie, time spanning Treatment Periods 1 to 3) will be presented for those randomized and receiving the same treatment in Treatment Periods 1 and 2. Separate summaries will be presented for Treatment Period 2 based upon the particular treatment sequence received in Treatment Periods 1 and 2: CHS-1420/CHS-1420, Humira/Humira and Humira/CHS-1420. Safety data for the open-label extension (Treatment Period 3) will be summarized based primarily upon events first recorded (or worsened in severity) during the open-label extension.

Study Duration	
Screening: up to 28 days
 
Treatment Period 1: 16 weeks (Week 0 to Week 16)
 
Treatment Period 2: 8 weeks (Week 17 to Week 24)
 
Treatment Period 3: 24 weeks (Week 25 to Week 48)
 
Follow-up: 8 weeks after last dose of study drug
 
Subjects may be considered completers if the subjects complete 48 weeks of treatment and the Follow-up visit 8 weeks following the last dose in this trial (completes the study);
 
Subjects may be withdrawn from study therapy for any of the following reasons:
 
• The subject experiences a serious adverse event (SAE) or medically important AE (e.g., serious or opportunistic infection) that would preclude further treatment with study drug;

[figure not shown]

Figure 1: Study Design

[figure not shown]

TABLE OF CONTENTS

SYNOPSIS	4
TABLE OF CONTENTS	13
LIST OF TABLES	15
LIST OF FIGURES	16

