7.1 Adverse Events

Adverse events will be collected, once the subject signs the ICF prior to undergoing Screening procedures, throughout the duration of the study. Treatment-emergent adverse events are those AEs starting after the subject receives the first dose of study drug. An AE is any unfavorable medical occurrence in a subject or clinical investigation subject administered a pharmaceutical product, which does not necessarily have to have a causal relationship with this treatment. An AE can therefore be any unfavorable and unintended sign, symptom, or disease temporally associated with the use of a medicinal (investigational) product, whether or not considered related to the medicinal (investigational) product. All AEs, including observed or suspected problems, complaints, or symptoms, are to be recorded on the appropriate eCRF. Documentation must be supported by an entry in the subject's source document. Each AE is to be evaluated for duration, severity, and causal relationship with the study drug or other factors.

Whenever possible, a specific disease or syndrome rather than individual associated signs and symptoms should be identified by the Investigator and recorded on the eCRF. However, if an observed or reported sign or symptom is not considered a component of a specific disease or syndrome by the Investigator, it should be recorded as a separate AE on the eCRF.

Any medical condition or signs or symptoms already present at Screening or Baseline should not be reported as an AE unless the medical condition or signs or symptoms present at Baseline worsen in severity or seriousness at any time during the study. In this case, it should be reported as an AE.

Clinically significant abnormal laboratory or other examination (e.g., ECG) findings that are detected during the study or are present at Baseline and significantly worsen during the study should be reported as AEs. The Investigator will exercise his or her medical and scientific judgment in deciding whether an abnormal laboratory finding or other abnormal assessment is clinically significant. Significant abnormal laboratory and other examination values occurring during the clinical study will be followed until repeat test results return to normal, stabilize, or are no longer clinically significant.

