7.1.1 Grading and Intensity of Adverse Events

The Investigator will rate the intensity of each AE as mild, moderate, severe, or life threatening.

Severity or Toxicity Grading:

Grade 1: Mild – An event that is usually transient in nature and generally not interfering with normal activities.

Grade 2: Moderate – An event that is sufficiently discomforting to interfere with normal activities.

Grade 3: Severe – An event that is incapacitating with inability to work or perform normal daily activity.

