8.2.3 Safety Analysis

Safety data will be summarized and listed. No inferential statistical analyses of the safety data are planned. All safety summaries and listings will be generated using the Safety Population based upon treatment received for the Treatment Period of interest.

Safety data through Week 16 will be presented by the treatment received (CHS-1420 or Humira). Safety data for the study as a whole will be presented for subjects receiving CHS-1420 during Treatment Period 1 and those receiving

Humira during Treatment Period 1. Separate summaries will also be presented for Treatment Period 2 based upon the particular treatment sequence received in Treatment Periods 1 and 2: CHS-1420/CHS-1420, Humira/Humira and Humira/CHS-1420.

Safety data for the open label extension will be summarized separately. The primary focus of these summaries will be events that are recorded after beginning open-label treatment and events that began in Treatment Period 1 or 2 and worsen in severity in Treatment Period 3. The events will be summarized by treatment received in Treatment Period 2 and overall.

Adverse events will be coded and classified by system organ class and preferred term using the Medical Dictionary for Regulatory Activities (MedDRA). Data summaries will be based on TEAEs. All TEAEs will be listed and summarized by the subjects' treatment group (Treatment Period specific) when the events were reported. A summary of all drug-related AEs will also be generated. If there are any SAEs or any AEs leading to the discontinuation of study drug, a separate data listing will be generated.

Clinical laboratory data will be summarized descriptively and listed by treatment (Treatment Period specific) group. The change from pre-dose to the end of the study will also be summarized. For selected laboratory assessments, the frequency of abnormal values will be tabulated where abnormal ranges are available.

Prior and concomitant medications will be coded with the World Health Organization Drug Dictionary (WHO-DD) and listed. All concomitant medication taken after first dosing of study drug will be summarized.

Vital sign and ECG data will be summarized and listed by dose group and visit.

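### Events that worsen after a period starts are counted for Treatment Period 3 but not for Treatment Period 2, so a Humira-onset event that worsens after the switch may be counted only under Humira

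*Combined protocol and SAP*

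**What the plan says.** For Treatment Period 3, Section 8.2.3 puts the focus on events recorded once open-label treatment has begun, together with "events that began in Treatment Period 1 or 2 and worsen in severity in Treatment Period 3". The Statistical Analysis part of the synopsis agrees, basing the extension summary mainly on "events first recorded (or worsened in severity) during the open-label extension".

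For Treatment Period 2, Section 8.2.3 says only this: "Separate summaries will also be presented for Treatment Period 2 based upon the particular treatment sequence received in Treatment Periods 1 and 2". The synopsis says the same in substance. Neither text mentions events that began earlier and worsened.

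Two general rules decide where an event goes by default. Section 7.1 defines emergence by onset: "Treatment-emergent adverse events are those AEs starting after the subject receives the first dose of study drug". Section 8.2.3 then places each such event by treatment group ("Treatment Period specific) when the events were reported").

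On recording, Section 7.1 says that a condition already there at Screening or Baseline is not an adverse event "unless the medical condition or signs or symptoms present at Baseline worsen in severity or seriousness at any time during the study". Section 7.1.1 adds: "The Investigator will rate the intensity of each AE as mild, moderate, severe, or life threatening".

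**The concern.** The sponsor recognised that worsening after a change of treatment matters, and wrote a rule for it, but only for the uncontrolled open-label period. The switch from Humira to CHS-1420 is randomized in Treatment Period 2. There the Humira/CHS-1420 sequence can be compared with subjects randomized to stay on Humira, and there the rule is absent.

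A subject may have a mild event on Humira in Period 1 that becomes moderate or severe after the switch. Under the default rules that event already emerged in Period 1 and was reported on Humira, so nothing in the text brings it into the Period 2 table. Section 2 makes the efficacy and safety of switching a secondary objective, so a type of event that could signal a problem with switching may be left out of the comparison meant to show it.

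**Working it through.** The plan gives no figure for worsening events, so there is nothing of its own to reproduce on this point. The check sets the texts side by side, then sizes the group concerned.

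**Step 1. Follow one event through the rules.** Take an event that starts on Humira in Period 1 and increases in severity in Period 2, after the switch.

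- Emergence (Section 7.1): it started after the first dose, so it is treatment-emergent from Period 1. The definition has no worsening element and does not restart with each period.
- Attribution (Section 8.2.3): it goes under the treatment at the time of reporting. If it was reported once, in Period 1, that is Humira.
- Period 2 summary (Section 8.2.3): split by sequence, with no rule that brings in earlier events that worsened.
- Reporting of worsening (Section 7.1): the instruction covers conditions "present at Baseline worsen in severity or seriousness at any time during the study". An event that began on study drug is not such a condition.

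Move the same increase in severity into Period 3 and the event is counted there, because the rule is written for that period.

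**Step 2. See whether another planned safety summary recovers it.**

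| Summary | Where switchers appear |
|---|---|
| Through Week 16 | Under Humira; ends before the switch |
| Whole study, Section 8.2.3 | Grouped by Period 1 treatment, so under Humira |
| Whole study, synopsis | Limited to subjects on the same treatment in Periods 1 and 2, so left out |
| Period 3 | Grouped by Period 2 treatment, so merged with CHS-1420/CHS-1420 |
| Period 2 by sequence | Their own group, beside Humira/Humira |

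Only the last row shows switchers beside the randomized non-switch arm.

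**Step 3. Work out the effect on the comparison.** Let *b* be the proportion with a Period 2 onset event, equal in the two Humira sequences. Let *w* be the proportion whose Period 1 event worsens in Period 2 without switching, and *w + d* that proportion with switching. For simplicity, take the two kinds of subject as separate.

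- Counting onset and worsening: (*b + w + d*) − (*b + w*) = *d*.
- Counting onset only: *b − b* = 0.

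The omission removes *d*. If *d* = 0, both counts give zero, so no difference is created.

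**Step 4. Size.** Inputs: about 250 subjects on Humira in Period 1 (Sections 4.3 and 8.3), half of whom switch (Section 4.3). Switchers: 250 / 2 = 125. The proportion with a Period 1 event that worsens after the switch is not in the documents, so it is assumed:

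- 1%: 125 × 0.01 = 1.25
- 2%: 125 × 0.02 = 2.5
- 5%: 125 × 0.05 = 6.25

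That is about 1 to 6 subjects. These are all the worsenings, not the excess due to switching, which could be smaller.

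**The case against.** The strongest reply is that the plan may capture these events without saying so. Section 7.1 requires the severity of each event to be evaluated, and adverse events are assessed at Weeks 16, 20 and 24. If sites enter a worsened event as a new record, the attribution sentence in Section 8.2.3 places it in Period 2 under CHS-1420. Serious events and those that led to stopping study drug get their own listings, and a reaction at a new injection site is a new event in any case. This stands, and it is why the conclusion is that such events may be counted only under Humira. It does not close the gap, because the result then depends on site practice that the protocol does not specify. The separate listings would also miss a non-serious worsening that does not stop treatment.

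Three stronger readings are tempting but not supported.

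- A reader might infer that each event carries a single severity rating, so that the data do not exist and the Period 3 rule cannot be carried out. Section 7.1.1 does not say whether intensity is rated once, at its worst, or again on change. The case report form pages are not in the documents, and the Period 3 rule presupposes that a change in severity can be identified.
- A reader might infer a bias in favour of CHS-1420. The silence applies equally to all three sequences. It can weaken a real excess after switching but, as Step 3 shows, does not produce a difference by itself.
- A reader might infer that the number affected rivals the number of severe events expected in Period 2. The documents give no such number.

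It is also fair to say that Section 8.2.3 plans no inferential safety analysis, so no formal test depends on this.

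**Conclusion.** The gap is real and limited. The worsening rule covers Treatment Period 3 and not Treatment Period 2, and the default definition and attribution rule do not fill the space. As written, a Period 1 event that worsens in Period 2 may be counted only under the Period 1 treatment, which for switchers is Humira. Any excess of worsening after the switch could then be diluted in the one planned safety table that sets switchers beside the randomized Humira/Humira arm.

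The size rests on an assumption: 1% to 5% of about 125 switchers gives roughly 1 to 6 subjects. The primary endpoint is untouched and the safety analysis is descriptive. It still deserves a change, because the safety of switching is a stated objective and the sponsor's own rule for the next period already supplies the remedy.

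**What to change.** In Section 8.2.3 and the synopsis, apply the Period 3 rule to Period 2 as well: count an event in the period in which it starts or increases in severity, and present the Period 2 counts by treatment sequence.

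To support this, state in Section 7.1 that an increase in severity of an event that began on study is captured with its date, either as a new record or as a dated severity change on the existing one.

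The cost is one sentence in each of Section 8.2.3 and the synopsis, one recording instruction, and slightly more adverse event records.

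Separately, and minor: Section 7.1.1 names four intensity categories but defines only three grades, with none for life-threatening. The two should be reconciled. This does not affect how events are attributed to periods.

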8.2.4 Immunogenicity Analysis

The immunogenicity of CHS-1420 will be evaluated using ECL assay that uses an incubation of acid-dissociated serum samples with biotinylated and SULFO-TAB CHS-1420 reagents and subsequent excitation of the SULFO-TAG via an electrochemical reaction and the luminescent readout that correlates with the level of human anti-CHS-1420 or anti-adalimumab antibodies present in the serum. These data will be summarized descriptively by treatment received.

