3 INVESTIGATIONAL PLAN

3.1 Overall Study Design and Plan

This is a 48 week study with a follow up visit 8 weeks after the last dose, randomized, double-blind, active-control followed by open label safety, parallel group, multicenter, study in subjects with active, moderate to severe, chronic PsO. Approximately 500 subjects will be randomized at approximately 160 sites worldwide.

The study will consist of 23 weeks of administration of blinded study drug over a 24 week period, divided into Treatment Period 1 (16 weeks) and Treatment Period 2 (8 weeks), 23 weeks of open label CHS-1420 during 24 weeks of Treatment Period 3 and a Follow-up visit 56 days (8 weeks) after the last dose of study drug. Subjects who meet inclusion/exclusion criteria will be stratified by body mass index (BMI) < 30 kg/m² or ≥ 30 kg/m² and by age < 65 years or ≥ 65 years. Within these strata, subjects will be randomized to receive either CHS-1420 or Humira. Half of the subjects assigned to Humira will be assigned to receive CHS-1420 in Treatment Period 2 with the remainder continuing on Humira. For simplicity, the assignments for Treatment Period 1 and Treatment Period 2 will be made at the beginning of Treatment Period 1.

In Treatment Period 1, subjects will receive 2 subcutaneous (SC) injections of study drug on Week 0/Day 0 followed by single SC injections of study drug every other week (QOW) from Week 1/Day 7 through Week 15/Day 105.

For Treatment Period 2, subjects will: 1) continue on CHS-1420 or 2) Humira or 3) will be switched from Humira to CHS-1420 and they will continue to receive single SC injections of study drug QOW from Week 17/Day 119 through Week 23/Day 161.

For Treatment Period 3, all subjects that complete Treatment Periods 1 and 2 and achieve at least a 50% improvement in PASI score (PASI-50) at Week 24 will receive 23 weeks of open-label CHS-1420 in Treatment Period 3 QOW from Week 25/Day 185 through Week 47/Day 329.

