4.3 Method of Assigning Subjects to Treatment Groups

Once the subject has signed the ICF at Screening, site personnel will assign a subject identification number (ID). The subject ID will include the site number (3 digits), and 3 digit subject number, assigned sequentially starting with 001. This number will be utilized to identify the subject throughout the study period. Once the subject ID has been assigned, the site will contact the Interactive Voice Response System/Interactive Web-based Response System (IXRS) to register the subject ID. Dropouts (subjects who discontinue study treatment early, and subjects who are randomized but not treated) will not be replaced. No individual is allowed to re-enter the study if previously randomized and dosed.

Subjects will be assigned to study drug in accordance with the randomization schedule generated using permuted block randomization by an independent statistician.

Approximately 500 subjects will be randomly assigned in a 1:1 ratio (approximately 250/arm) to receive 1 of the following treatments in Treatment Period 1:

- 2 SC injections (2 pre-filled syringes, [80 mg]) of Humira on Week 0/Day 0 and 1 SC injection (1 pre-filled syringe [40 mg]) of Humira QOW from Week 1/Day 7 through up to Week 15/Day 105.
- 2 SC injections (2 pre-filled syringes, [80 mg]) of CHS-1420 on Week 0/Day 0 and 1 SC injection (1 pre-filled syringe [40 mg]) of CHS-1420 QOW from Week 1/Day 7 through up to Week 15/Day 105.

Subject randomization will be stratified by body mass index (BMI) (less than ($<$) 30 kg/m² or greater than or equal to (\geq) 30 kg/m²), age (<65 yrs or ≥ 65 yrs) and region.

At the end of Treatment Period 1 (Week 16), subjects taking Humira will either begin dosing with CHS-1420 or continue with Humira during Treatment Period 2. A single randomization will be used to determine treatment in Treatment Periods 1 and 2. In effect, a 2:1:1 randomization will be used where for each 2 subjects randomized to receive CHS-1420 an additional 2 will be assigned to receive Humira in Treatment Period 1. For the subjects assigned to Humira in Treatment Period 1, 1/2 of these will be randomly assigned to continue with Humira for Treatment Period 2 and 1/2 will be assigned to switch to CHS-1420 for Treatment Period 2.

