At the end of Treatment Period 2 (Week 24), all subjects that achieve at least a PASI-50 score will be assigned CHS-1420 for Treatment Period 3 and continue QOW administration from Week 25/Day 175 through Week 47/Day 329.

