7.2.11 Anti-Drug Antibody Assessment

Antibodies to adalimumab will be measured in the sera of subjects enrolled in this study to compare the immunogenicity of CHS-1420 to that of Humira.

Immunogenicity will be evaluated over the course of the study. Comparison of immunogenicity will be made at Weeks 0/Day 0 (pre-dose), 2, 4, 8, 12, 16, 20, 24, 32, 40, 48 and at the ET or Follow Up visit 56 days/8 weeks after the last dose of study drug.

The immunogenicity testing will be performed using validated ECL ADA assays. Presence of ADA based on this confirmatory assay will be compared between groups. An assay to determine if ADAs are neutralizing may be used.

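### After Week 16 the ADA summaries are grouped by treatment received rather than by sequence, so antibodies carried over from Humira can be counted under CHS-1420, and from Week 25 no group is still on Humira

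*Combined protocol and SAP*

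**What the plan says.** All references are to the combined protocol and SAP.

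- **Purpose.** Section 7.2.11 measures antibodies "to compare the immunogenicity of CHS-1420 to that of Humira". On timing it says: "Comparison of immunogenicity will be made at Weeks 0/Day 0 (pre-dose), 2, 4, 8, 12, 16, 20, 24, 32, 40, 48", and it adds the ET or Follow-up visit.
- **Grouping.** Section 8.2.4, after describing the assay, says: "These data will be summarized descriptively by treatment received". It does not define the phrase. It mentions no treatment sequence and no treatment period, and has no rule for subjects already positive at Week 16.
- **Other outcomes.** Section 8.2.2 (efficacy) and Section 8.2.3 (safety) both present Treatment Period 2 data by the sequence received over Periods 1 and 2, giving three groups. For safety data through Week 16, 8.2.3 uses treatment received and names two groups, CHS-1420 or Humira.
- **Switch.** Section 4.3 says of the Humira arm: "1/2 of these will be randomly assigned to continue with Humira for Treatment Period 2 and 1/2 will be assigned to switch to CHS-1420".
- **Extension.** Under Section 4.3, "all subjects that achieve at least a PASI-50 score will be assigned CHS-1420 for Treatment Period 3". Section 8.1.5 labels the extension population by the arm received in Period 2.
- **Objectives.** The efficacy and safety of switching from Humira to CHS-1420 is a secondary objective (synopsis and Section 2).

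**The concern.** A positive ADA result does not necessarily clear when the product changes. If a subject becomes positive on Humira before Week 16, switches, and is still positive at Week 20, a table grouped by the product then being taken places that result under CHS-1420. The column mixes three things: antibodies formed on CHS-1420 from the start, antibodies formed on Humira and still detectable, and antibodies that first appear after the switch. The third is what the switching objective needs, and such a table cannot isolate it.

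The later visits raise a separate issue. Section 7.2.11 lists comparisons through Week 48 and beyond, but in Treatment Period 3 every continuing subject takes CHS-1420. A contrast between products on treatment is not available there.

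**Working it through.** **1. Group sizes.** The ADA analysis states no figure of its own, so the counts come from Sections 8.3 and 4.3. Check of 8.3: response 70% in both arms, margin 15 points, 95% two-sided interval, 90% power, true difference zero.

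n per arm = 2 × 0.7 × 0.3 × (1.960 + 1.645)² / 0.15² = 242.6, so 243.

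Power at 250 per arm is 91.1%. The plan's approximate 250 per arm is reproduced.

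**2. Allocation (4.3), no dropout assumed.** The effective ratio is 2:1:1 of 500:
- CHS-1420 throughout: 250
- Humira in both periods: 125
- Humira, then CHS-1420: 125

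**3. Groups under the plain reading of 8.2.4.**

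| Visits | CHS-1420 column | Humira column | Prior Humira within CHS-1420 column |
|---|---|---|---|
| Through Week 16 | 250 | 250 | 0 |
| Weeks 20, 24 | 250 + 125 = 375 | 125 | 125/375 = 33.3% |
| Weeks 32, 40, 48 | up to 500 | 0 | 250/500 = 50% |

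**4. Carried-over positives at Weeks 20 and 24.** The documents give no ADA rate and do not say how long positivity lasts. Assume Humira prevalence h at Week 16 and full persistence. The number counted under CHS-1420 is 125 × h:
- h = 10%: 12.5
- h = 30%: 37.5
- h = 50%: 62.5

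Partial persistence lowers these in proportion.

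**5. Effect on the product contrast.** Let c be the rate in subjects always on CHS-1420, and assume switchers keep the Humira rate h.

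Apparent difference = (250c + 125h)/375 − h = (2/3)(c − h).

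A true difference of 5, 10 or 15 points would show as 3.3, 6.7 or 10.0.

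**6. Visibility of new antibodies after switching.** Suppose conversion among previously negative switchers doubled from an assumed 5% to 10%. The pooled column would move by 0.05 × (1 − h) × 125/375:
- h = 10%: 0.045 × 1/3 = 1.5 points
- h = 50%: 0.025 × 1/3 = 0.8 points

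**7. Later visits.** Section 3.1 says that subjects who complete Periods 1 and 2 with at least PASI-50 at Week 24 "will receive 23 weeks of open-label CHS-1420 in Treatment Period 3". Section 5.2.5 reserves the Follow-up visit for subjects who complete Week 48, so their last drug is also CHS-1420. Week 24 is the last scheduled visit with a Humira group still on treatment.

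**The case against.** The best defence is that 8.2.4 is shorthand. ADA assessment sits in Section 7, Safety Measurements. Section 8.2.3 bases all its safety summaries on treatment received for the period concerned, and then sets out the three sequences for Period 2. On that reading ADA would be shown by sequence too. This stands as a possible reading, but the text does not settle it: 8.2.4 is a separate section with its own rule, and the synopsis lists immunogenicity apart from safety. Even sequence tables would not separate new positives from those present at Week 16.

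Three stronger inferences are tempting, and the documents do not support them.

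- *That Humira antibodies will certainly be tabulated as CHS-1420 positives.* This needs the plain reading of an undefined phrase, and persistence, on which the documents are silent.
- *That no Humira group of any kind exists at Weeks 32 to 48 or after.* Under 8.1.5, and the extension rules in 8.2.2 and 8.2.3, up to 125 subjects could carry a Period 2 Humira label. They would be taking CHS-1420, and the group labelled CHS-1420 would still include switchers. ET samples may also come from subjects who stopped on Humira, but these are selected by having stopped. Section 7.2.11 does not name the groups compared at each visit; the product contrast comes from its opening statement of purpose.
- *That the table would set a large prevalence against a small switch effect.* With 5% conversion among negative switchers, positivity within the switch arm would be 10% + 4.5% = 14.5% or 50% + 2.5% = 52.5% at the two ends of the assumed range. That describes the 125 switchers, not the pooled column of 375, and every input is assumed.

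It is also fair that the ADA summaries are descriptive, that no decision rule rests on them, and that the data can be re-tabulated later without loss.

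**Conclusion.** The point holds as a gap in the grouping rule after Week 16 that should be closed. On the plain reading, one third of the CHS-1420 column at Weeks 20 and 24 had 16 weeks of Humira first, and nothing distinguishes antibodies present at the switch from those that follow it. The number of carried-over positives is unknown; about 12 to 62 is an illustration that rests on 10% to 50% Humira prevalence and full persistence, both assumed. At Weeks 32 to 48, and at Follow-up for Week 48 completers, no group is still on Humira, so any comparison there is between treatment histories and not between products being taken.

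The effect is limited to descriptive ADA summaries after Week 16. The randomised ADA comparison through Week 16 and the primary PASI-75 analysis are unaffected.

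**What to change.** 1. **Section 8.2.4.** Summarise ADA through Week 16 by Period 1 treatment. From Week 20, summarise by treatment sequence received, with the three groups already used in 8.2.2 and 8.2.3.
2. **Section 8.2.4.** Add the number of subjects newly ADA-positive at Weeks 20 to 24 among those negative through Week 16, for Humira/CHS-1420 against Humira/Humira. These sub-arms come from the original randomisation, and the Week 16 sample (Day 112) precedes the Period 2 dose that Sections 3.1 and 5.2.3 place at Day 119. Section 4.5 gives Day 105 for the start of the Period 2 injections and needs to be reconciled with those sections.
3. **Section 7.2.11.** Limit the CHS-1420 versus Humira comparison to visits through Week 24, and describe later visits by sequence only.

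**Cost.** Wording and a few more tables; the samples are already scheduled. The groups are smaller, about 125 per Humira sub-arm. Counts of new positives would be low: at the assumed 5% conversion, 125 × 0.9 × 0.05 = 5.6 subjects or 125 × 0.5 × 0.05 = 3.1 subjects in the switch arm. The result should therefore be reported as descriptive.
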